5.5.9 Unscheduled Visits/Lead Replacements

Unanticipated complications related to the PNS system may occur, including technical issues with the device, assistance with bandage change or lead exit site care, or adverse events requiring further evaluation by study staff. Most issues may be addressed by telephone. Subjects may return to clinic for further evaluation if necessary. Based on the discretion of the subject and study investigators, a decision may be made to allow the subject to continue in the study or be discharged.

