2.2 Literature Review

PNS has been studied for the treatment of some chronic pain syndromes (7, 17-19), including persistent post-amputation pain. The mechanism of action of peripheral nerve stimulation in pain relief is commonly explained using the "gate control theory" of Melzack and Wall (20). This theory explains that electrical current-induced activation of large-diameter myelinated afferent peripheral nerve fibers inhibits the transmission of pain signals from small-diameter pain fibers to the central nervous system at the level of the spinal cord (15). Rauck et al (7) showed that 9 of 14 subjects who completed two-weeks of PNS therapy reported reductions in mean daily worst post-amputation pain, average RLP and PLP, and interference from RLP and PLP at least one month after the end of treatment. Interference from RLP or PLP refers to how pain has interfered with general activity, mood, walking ability, work, relations with others, sleep, and enjoyment of life. PNS was shown to be effective in reducing post-amputation pain when most pain is confined to one or two nerve distributions (7, 21-22). Results showed that 14 of 16 subjects reported ≥75% paresthesia coverage from PNS, obtained clinically significant pain relief, and proceeded to a 2-week home trial with this system. 9 subjects completed the 2-week trial and 5 subjects did not complete the trial because

- of accidental dislodgement (N=2), temporary discomfort near the lead (N=2), and return of post-amputation
- 91 pain despite stimulation (N=1). The 9 responders who completed the home trial reported reductions in their
- mean daily worst post-amputation pain ($56 \pm 26\%$, $56 \pm 26\%$, N = 9), average residual limb pain ($72 \pm 26\%$)
- 93 28%, $42 \pm 27\%$, N = 7), average phantom limb pain $(81 \pm 28\%, 47 \pm 48\%, N = 7)$, interference from residual
- 94 limb pain $(81 \pm 27\%, 53 \pm 17\%, N = 6)$, interference from phantom limb pain $(83 \pm 31\%, 56 \pm 46\%, N =$
- 95 7), and Pain Disability Index (PDI) $(70 \pm 38\%, 55 \pm 32\%, N = 9)$ during the 2nd week of stimulation and 4
- 96 weeks after the end of stimulation, respectively. All 9 responders rated their change in quality of life as
- 97 improved at the end of stimulation and at the end of the 4-week follow-up period.

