5.5.6 Visit 7, 8, and 9: Weekly follow-up telephone evaluations

Visits 7, 8, and 9 consist of weekly telephone evaluations at 5, 6, 7 weeks after starting peripheral nerve stimulation (Group 1) or discontinuation of peripheral nerve block (Group 2). If issues related to the

peripheral nerve stimulator device or leads occur that cannot be resolved by telephone, subjects may be evaluated in the Interventional Pain Clinic if needed.

Subjects are asked to rate their worst, least, and average PLP and RLP (BPI #3, #4, and #5). A medical reconciliation will be completed during each phone evaluation by asking the subject how many pills of narcotic pain medications they have left and querying the Virginia Prescription Monitoring Program Database.

5.5.7 Visit 10: Second outpatient clinic evaluation / up to 60 days after start of PNS

All subjects are asked to return to the Interventional Pain Clinic at approximately 60 days after starting peripheral nerve stimulation (Group 1) or discontinuation of peripheral nerve block (Group 2). Stimulator leads will be removed by gentle traction. The lead will be visually inspected by study staff to evaluate for lead fracture. In the case of a retained lead fragment, study staff will determine the most appropriate medical plan to further evaluate and treat the subject. In most instances, retained lead fragments do not need to be removed and are rarely associated with further complications. Lead exit sites are inspected for skin irritation, infection, and inflammation. Both groups will continue to be treated with SMT as needed until the end of participation in the study. Subjects in Group 1 are encouraged to complete the entire 60-days of peripheral nerve stimulation, however are free to discontinue treatment at any time during the treatment phase.

5.5.8 Visits 11, 12, and 13: Phone evaluations at 3, 6, and 12 months after study enrollment

Telephone evaluations for both groups occur at approximately 3, 6, and 12 months after study enrollment. Outcome measures to be assessed are listed in the Schedule of Study Procedures.

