- The duration of this investigation is expected to be 18-24 months. We anticipate enrolling 2-4 patients per 454
- month. Each patient's participation will last approximately 12 months. 455

Data Management 6.0

Sample Size

- The investigation seeks to broaden the knowledge of the effects of neuromodulation on acute post-operative 458
- pain in nontraumatic lower extremity amputation. The aim is to evaluate the feasibility of implementing 459
- PNS in TFA or TTA in the acute post-operative period. 16 subjects will be randomized into two groups 460
- 461 with 8 each. Sampling will not be restricted by race or gender. The sample size of 16 is expected to allow
- the investigators to conduct a cost-effective yet informative pilot study to assess the logistics of placing the 462
- 463 device as described in this protocol, evaluate safety, and report any clinically significant differences in
- primary and secondary outcomes between Treatment and Control Groups. The study outcomes will be 464
- 465 reported in nontraumatic TFA or TTA, many of which are secondary to dysvascular disease. Although this is a specific subset of all amputations that are performed, dysvascular disease accounts for a sizeable 466
- proportion of limb loss in the US with an estimated prevalence of 38-82% (24, 25). The results of this 467
- investigation will be used to refine the study design, recruitment, randomization, retention, and assessment 468
- 469
 - procedures, and ultimately develop a larger, multicenter, randomized controlled trial to further evaluate

470 treatment efficacy, adverse effects, and cost efficiency. To improve generalizability, subsequent

471 investigations will seek to include a wider subset of amputations which may be accomplished with the

472 addition of more study sites.

473

490

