8.0 Data and Safety Monitoring

Primary and secondary outcomes will be recorded at each follow-up visit. Study investigators will retain study-related documents in double-locked filed cabinet in 2C-117. The PI or an investigator will conduct a data and safety monitoring review once every 8 weeks in which Case Report Forms and any AE forms are evaluated. Safety information is also assessed at outpatient study visits and by telephone calls. If study investigators determine that the PNS treatment is unsafe to continue (i.e. systemic infection, increased pain that is intolerable to the subject, need for implantable electronic device that requires discontinuation of the PNS), then PNS will be discontinued as appropriate.

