8.1 Serious Adverse Events

Serious Adverse Events (SAE) will be recorded on Form AE and the IRB will be notified within 5 days of occurrence. Monitoring for SAEs will occur at each follow-up encounter. Subjects will be asked if they are experiencing any increased discomfort, pain, skin irritation, or bleeding. At the outpatient follow-up visits, the PNS lead exit site will be examined and the stimulator device will be interrogated to ensure proper functioning. Any adverse event will be investigated and managed as appropriate. Subjects are instructed to notify study personnel by [contact]) in case of any changes in medical status as soon as possible. If investigators need to be reached after normal business hours, subjects will be given instructions on how to page study staff who call the subject as soon as possible.

Details regarding any observed adverse event and its relation to the PNS system will be collected on Form AE. The severity of the AE will be classified as mild (event that causes mild discomfort or inconvenience and resolves without treatment), moderate (event that requires medical intervention or medication to treat), or severe (event that requires intervention to prevent permanent impairment or damage, an event that requires or prolongs hospitalization, or an event that is disabling, causing permanent damage, life threatening, or causing death). Any treatment necessary related to the AE will be documented. AEs will be followed to resolution, even if a subject is discharged from the study early. Adverse events will be documented and reported so that the safety profile of this system may be further understood.

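### Section 5.5.9 allows discharge from the study after a PNS complication, without criteria and in Group 1 only, so later outcome data may be lost in one arm

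*Combined protocol and SAP*

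**What the plan says.** Section 5.5.9 opens with the trigger: "Unanticipated complications related to the PNS system may occur". Its examples are technical problems, help with bandages or the exit site, and adverse events that need evaluation. It expects most of these to be settled by telephone. For the rest it relies on shared judgement, in the words "Based on the discretion of the subject and study investigators". Two outcomes are open, since the choice is one "made to allow the subject to continue in the study or be discharged". It gives no criteria.

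Section 8.1 confirms that this kind of exit is from the study and states what continues afterwards: "AEs will be followed to resolution, even if a subject is discharged from the study early". No section seen says that BPI scores or medication data are still collected after discharge.

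Elsewhere the protocol treats stopping the device as a separate matter. Section 5.5.7 says that Group 1 subjects are "free to discontinue treatment at any time during the treatment phase". Section 8.0 says that if treatment is judged unsafe, "then PNS will be discontinued as appropriate". Neither says that the subject then leaves the study.

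On size and analysis, section 6 states that "16 subjects will be randomized into two groups", 8 in each, and that subjects are not blinded. Section 6.3 names a two-sample t-test with unadjusted p-values. It defines no analysis set, no as-randomised rule and no handling of missing data.

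**The concern.** A route out of the study that only a device complication can open cannot apply to controls. Randomisation takes place at consent and enrolment (6.2), before lead placement (5.5.2), so every such exit is a post-randomisation loss from one arm. Those who decide know the allocation.

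Some of the complications the protocol expects are close to the outcome. Section 7.2 classes lead migration or dislodgement, and worsening pain, as common, which it defines as more than 10%. If discharge tends to follow poor pain control, the Group 1 subjects who remain would look better than the group that was randomised.

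Acute and chronic pain are the primary outcomes (4.1), retention is a stated feasibility objective (1.2), and the results are meant to shape a larger trial (6.1). The 3-, 6- and 12-month assessments in 5.5.8 are telephone calls made after the leads are out, so a device problem is no reason to stop them.

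**Working it through.** **No figure in the plan to reproduce.** The 16 subjects are justified as a pilot. No power, effect size, SD or dropout allowance is given.

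**Step 1: what the text settles.**

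| Question | Section | Answer |
|---|---|---|
| What opens the route? | 5.5.9 | A PNS-system complication, so Group 1 only |
| Who decides? | 5.5.9 | Subject and investigators; no criteria |
| Discharged from what? | 5.5.9, 8.1 | The study |
| What follow-up is promised afterwards? | 8.1 | Adverse events |
| Does stopping PNS mean leaving? | 5.5.7, 8.0 | Not stated; only treatment stops |
| Are discharged subjects kept in the analysis? | 6.3 | Not stated either way |

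**Step 2: shift in the Group 1 mean.** Let the 8 − k subjects kept have mean m, and let the k subjects lost have a mean of m + D had they been followed. The mean of all 8 is m + kD/8. Analysing only those kept lowers it by kD/8. This assumes that the lost subjects contribute nothing to the comparison in question. The documents give no value for k or D, so both are assumed.

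| k lost | D = 0 | D = 1 | D = 2 | D = 3 | D = 4 |
|---|---|---|---|---|---|
| 1 | 0 | 0.125 | 0.25 | 0.375 | 0.5 |
| 2 | 0 | 0.25 | 0.5 | 0.75 | 1.0 |
| 3 | 0 | 0.375 | 0.75 | 1.125 | 1.5 |

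For k = 3 and D = 2: 3 × 2 / 8 = 0.75 points on the 0–10 scale.

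**Step 3: is k = 3 conceivable?** Section 2.2 reports an earlier study of this system in which 5 of 14 did not complete a 2-week home trial, because "of accidental dislodgement (N=2), temporary discomfort near the lead (N=2), and return of post-amputation" pain in one. That is 5/14 = 36% (exact 95% CI 13% to 65%). Applied to 8 subjects, it gives 8 × 5/14 = 2.9, with binomial probabilities of 97% for at least 1, 84% for at least 2 and 59% for at least 3. Return of pain alone gives 8 × 1/14 = 0.6. These are counts of stopping stimulation, not of leaving a study, so they show only that k = 3 is conceivable.

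**Step 4: effect on the t-test.** This was simulated with 100,000 runs, no true effect, 8 controls and k of 8 Group 1 subjects dropped. A two-sided 5% level was assumed, since the plan states none. Negative bias favours PNS.

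| Link between being dropped and pain | Bias in SD, k = 1 / 2 / 3 | Type I error, k = 1 / 2 / 3 |
|---|---|---|
| None | 0 / 0 / 0 | 5.0% / 5.0% / 5.0% |
| Correlation 0.5 | −0.10 / −0.19 / −0.27 | 5.7% / 6.5% / 7.6% |
| Exactly the worst scores dropped | −0.21 / −0.38 / −0.55 | 7.7% / 12.0% / 17.0% |

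Even with no link to pain, going from 8 v 8 to 8 v 5 raises the difference detectable with 80% power from 1.51 to 1.75 SD.

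**The case against.** The strongest reply is that the protocol already largely separates treatment from participation. The case nearest to a pain failure, intolerable increased pain, is dealt with in 8.0 by stopping PNS. A dislodged lead may be replaced (5.5.2, 7.2.3). Poor pain relief is not among the events listed in 5.5.9, and a subject who chooses to leave is an ordinary withdrawal. This stands as a limit on how often the route would be used. It does not explain why 5.5.9 links a device complication to leaving the study at all.

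A reader might go further and infer that the plan removes PNS failures from the comparison. The documents do not support that:

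- Section 6.3 does not say that discharged subjects are dropped. Scores recorded before discharge could still enter the monthly means.
- Outcomes taken from the medical record (4.2.7) do not depend on contact with the subject.
- Only 1 of the 5 non-completers in the cited study stopped because pain returned. Two had accidental dislodgement and two had temporary discomfort.
- The decision is shared with the subject and is not the investigator's alone.

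Nor is there support for saying that the pilot would understate non-retention. A discharged subject can be counted as not retained, and nothing excludes such subjects from that count. Controls can also be lost, by other routes.

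Part of the text between section 5.6 and the statement of study duration was not available here, so a withdrawal rule in that place cannot be ruled out.

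**Conclusion.** The concern holds as a risk that the text permits, not as a demonstrated bias. Section 5.5.9 provides a Group 1-only exit without criteria, 8.1 promises only adverse-event follow-up afterwards, and 6.3 does not commit to analysis as randomised. Together these allow one-sided loss of later pain, opioid and chronic-pain data that could be related to outcome.

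The size is unknown. The 0.75-point figure rests on an assumed k = 3, an assumed D = 2 with no source in the documents, and lost subjects contributing no data. If discharge is unrelated to pain, the bias is zero and only precision suffers. It should not be read as a forecast, and 5 of 14 should not be read as an expected discharge rate.

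The feasibility aim and the small sample temper the seriousness. The change is a cheap improvement, worth making because pain is the primary outcome and retention is something the pilot sets out to assess.

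**What to change.** 1. Reword 5.5.9 so that a device complication can end device use but not study follow-up, in line with 5.5.7 and 8.0. Decisions about the device itself stay where the protocol places them.
2. State that all scheduled BPI and medication assessments continue to 12 months after a device problem, unless the subject withdraws consent. This is the main part of the repair, since an as-randomised rule cannot supply scores that were never collected.
3. State in 6.3 that all randomised subjects are analysed in their assigned group, including those in Group 1 who never receive a lead or stop PNS early.
4. Report discharges and withdrawals by arm, with reasons and timing, as part of the retention result.

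The cost is a few sentences in 5.5.9 and 6.3 and a few follow-up calls that are already in the schedule.

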5.6 Facilities and Resources

- Subjects will be screened at the Vascular Clinic. Lead placement will take place in the Interventional Pain
- Clinic (IPC) or at the subject's bedside. Study data, recruitment materials, and sensitive patient information
- will be stored in a fixed, locked file cabinet in the IPC in 2C-117. Peripheral nerve stimulators and all
- related materials will be stored in a locked cabinet in the IPC. Devices will be labeled and designated
- specifically for research purposes. Only these labeled devices may be used in the study.
- 421 Study investigators who have received necessary training on the study procedures will be performing the
- placement of the peripheral nerve stimulator lead wire. Procedures include but are not limited to: (1)
- placement of stimulator lead under ultrasound guidance, (2) removal of stimulator lead at the end of the 30
- 424 to 60-day treatment period (3) replacement of stimulator lead (if applicable).

- The duration of this investigation is expected to be 18-24 months. We anticipate enrolling 2-4 patients per 454
- month. Each patient's participation will last approximately 12 months. 455

Data Management 6.0

Sample Size

- The investigation seeks to broaden the knowledge of the effects of neuromodulation on acute post-operative 458
- pain in nontraumatic lower extremity amputation. The aim is to evaluate the feasibility of implementing 459
- PNS in TFA or TTA in the acute post-operative period. 16 subjects will be randomized into two groups 460
- 461 with 8 each. Sampling will not be restricted by race or gender. The sample size of 16 is expected to allow
- the investigators to conduct a cost-effective yet informative pilot study to assess the logistics of placing the 462
- 463 device as described in this protocol, evaluate safety, and report any clinically significant differences in
- primary and secondary outcomes between Treatment and Control Groups. The study outcomes will be 464
- 465 reported in nontraumatic TFA or TTA, many of which are secondary to dysvascular disease. Although this is a specific subset of all amputations that are performed, dysvascular disease accounts for a sizeable 466
- proportion of limb loss in the US with an estimated prevalence of 38-82% (24, 25). The results of this 467
- investigation will be used to refine the study design, recruitment, randomization, retention, and assessment 468
- 469
 - procedures, and ultimately develop a larger, multicenter, randomized controlled trial to further evaluate

470 treatment efficacy, adverse effects, and cost efficiency. To improve generalizability, subsequent

471 investigations will seek to include a wider subset of amputations which may be accomplished with the

472 addition of more study sites.

473

490

6.2 Sampling and Randomization Procedures

Based upon historical data on amputations at the HHM-VAMC, there are estimated to be one to two 474 475 amputations per week that would qualify for enrollment in this study. Subjects will be screened for enrollment through the vascular surgery clinic. A considerable proportion of vascular clinic patients will 476

require lower extremity amputation and are usually scheduled for next day surgery due to the urgency of 477

presentation. Study investigators will conduct a chart review of potential subjects and complete Form 01-478

479 A (screening and demographic information). Based on the chart review, if a patient appears to meet all 480

eligibility criteria, then they will be contacted by study investigators for potential enrollment. If the patient

agrees to participate, they will be consented and randomized to Group 1 or Group 2. 481

482 Prior to the start of this study, a member of the study staff that is not involved with recruitment or data

483 evaluation will be responsible for generating a random string of group assignments long enough to fill all

anticipated spots in this study. The numbers will be placed in secure envelopes by blocks of two. A block 484

485 of two will contain one assignment to the Treatment Group and one assignment to the Control Group. As

486 subjects are consented and enrolled in the study, they will be assigned an envelope which randomizes them

487 to a group. Subjects are not blinded to their group assignments. Subjects in the Treatment Group will

receive the investigational treatment (30 to 60-days of peripheral nerve stimulation) in addition to SMT. 488

489 Subjects in the Control Group will be treated with the SMT alone.

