3.2 Study Design

- This prospective randomized controlled trial aims to assess the feasibility of using a novel percutaneous
- peripheral nerve stimulator system to produce clinically significant reductions in acute post-surgical pain
- after nontraumatic lower extremity amputation, and evaluate reductions in the incidence and/or severity of
- chronic PLP or RLP. Subjects who have moderate pain 2 to 7 days after transfemoral or transibial
- amputation surgery will be enrolled and randomized to Group 1 ("Treatment Group") or Group 2 ("Control
- Group"). Subjects in Group 1 will be treated with 30 to 60 days of PNS in addition to SMT. Subjects in
- Group 2 will be treated with the SMT alone. SMT is defined as the same routine medical care given to all
- patients, regardless of whether they are enrolled in the study. This may include, but is not limited to non-
- opioid and opioid pain medications, regional anesthesia peripheral nerve blockade, daily postoperative
- visits by the Acute Pain Service, and follow-up appointments in the Interventional Pain Clinic.
- Group 1: 30 to 60 days of peripheral nerve stimulation starting within 7 days after surgery and Standard Medical Therapy
 - Group 2: Standard Medical Therapy only
- Subjects are evaluated daily by study investigators from the time of study enrollment to hospital discharge.
- 30 Subsequent telephone or outpatient clinic evaluations occur at intervals which are detailed in the Schedule
- of Study Procedures (Appendix).

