5.4 Eligibility

5.4.1 Inclusion Criteria

Inclusion criteria are nontraumatic transfemoral or transtibial amputation (TFA or TTA, respectively) and age over 18..

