Patients who are interested in participation will be asked to complete a Beck Depression Inventory (see Form BDI) to be screened for depression (must score 20 or less) prior to enrollment. Veteran participants who are evaluated by study staff and suspected to be depressed will be further evaluated by a psychiatrist or psychologist utilizing the Mental Health Consultation and Liaison Service at McGuire VAMC. Research study staff will page the C&L service at [name] (Use [name] after 4pm and on weekends) and then walk the participant to the C&L provider to facilitate the evaluation on the day that the participant

presents as depressed. If non-veterans participants are enrolled, arrangements made for him/her to be evaluated at a non-VA facility.

[figure not shown]

Figure 1 Subject flowchart.

258

259

260261

Patients who agree to participate in the study will be asked to sign the Consent Form. Ideally, patients should provide informed consent and be enrolled in the study prior to surgery. Typically, the local anesthetic peripheral nerve block catheters (or single shock femoral or sciatic nerve blockade) are placed on the day prior to surgery or day of surgery. Subjects will be given the opportunity to enroll in the study when the catheter is placed, however, those who wish to decide on enrollment after their surgery may be enrolled up until the time in which their peripheral nerve block catheter is removed, which is usually by post-op day 5. Upon enrollment, subjects will be evaluated by APS daily.

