5.5.1 Visit 1: 24-48 hours after removal of peripheral nerve block catheter

Subjects will be assessed at least 24-48 hours after removal of the peripheral nerve catheter (or after the effects of a single shot femoral and/or sciatic nerve block have worn off). They will be evaluated for post-surgical complications, and for the presence of phantom limb sensation or pain and RLP. Average pain severity and anatomic distribution will be reported by answering BPI-SF #2 and #5.

Subjects in Group 1 will proceed to Visit 2 and undergo placement of the peripheral nerve stimulator lead(s) by post-op day 7, in addition to receiving SMT. Subjects in Group 2 will skip to Visit 3. They will be treated with SMT and followed up by study investigators daily until discharged. They will subsequently be followed up by telephone according to the Schedule of Study Procedures.

5.5.2 Visit 2A: Placement of percutaneous peripheral stimulator leads (Group 1

only)

Subjects randomized to Group 1 proceed to placement of the stimulator leads by post-op day 7 to begin peripheral nerve stimulation therapy with the SPRINTTM PNS System (Figure 2.1). The procedure for placement of the peripheral nerve stimulator lead (Figure 2.2) is similar to placement of a peripheral nerve catheter for local anesthetic blockade. The main difference is that instead of delivering medications, electrical stimulation is applied to the peripheral nerve over a wide range of parameters. Also, the stimulator lead does not need to be placed as close to the nerve as a local anesthetic peripheral nerve catheter. This study will evaluate the application of one or two leads per subject: one for the femoral nerve and/or one for the sciatic nerve. Lead placement is expected to take up to 2 hours.

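### Section 6.2 assigns the group at consent, preferably before surgery, while 3.2 and the Appendix randomize after surgery; for pre-operative consenters, assignment precedes the baseline scores and any new systemic infection

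*Combined protocol and SAP*

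**What the plan says.** Section 6.2 (Sampling and Randomization Procedures) gives the timing twice. After eligibility by chart review, if the patient "agrees to participate, they will be consented and randomized to Group 1 or Group 2". Later, as "subjects are consented and enrolled in the study, they will be assigned an envelope which randomizes them" to a group. It adds that subjects are not blinded and that envelopes come in blocks of two.

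Section 5.5 (Study Plan) says when consent should happen: "Ideally, patients should provide informed consent and be enrolled in the study prior to surgery". Later enrolment is allowed until the block catheter is removed, usually by post-operative day 5. The end of 5.5 gives no time for randomization and sends the reader to 6.2.

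Two other places give a different time. Section 3.2 (Study Design) reads "Subjects who have moderate pain 2 to 7 days after transfemoral or transibial" and continues "amputation surgery will be enrolled and randomized to Group 1" or Group 2. The Schedule of Study Procedures in the Appendix marks Randomize under Visit 1 (Baseline), not under Screen and Consent.

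The pain condition in 3.2 is not a listed criterion. Section 5.4.1 reads: "Inclusion criteria are nontraumatic transfemoral or transtibial amputation (TFA or TTA, respectively) and age over 18". Systemic infection is an exclusion in 5.4.2.

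At Visit 1, section 5.5.1 says of subjects: "They will be evaluated for post-surgical complications, and for the presence of phantom limb sensation or pain and RLP". It then states: "Subjects in Group 1 will proceed to Visit 2 and undergo placement of the peripheral nerve stimulator lead(s) by post-op day 7". No step between these two sentences makes placement depend on what the evaluation finds.

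**The concern.** The plan contains two randomization times, and staff are referred to the earlier one. Three things depend on which is used.

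- **Population.** Before surgery, post-operative pain does not exist, so assignment at that time cannot select the population that 3.2 describes.
- **Baseline.** The Appendix schedules BPI, PDI and PCS at Visit 1. Under 6.2 an unblinded subject can give these self-reports already knowing the group. Section 6.3 compares within-subject changes in pain between groups, so a baseline coloured by that knowledge enters the comparison.
- **One-sided non-treatment.** Section 7.3 relies on excluding systemic infection to limit the risk of needle insertion. If infection appears after assignment, clinicians would probably withhold the lead. Only Group 1 faces that decision; a Group 2 subject in the same state continues as planned. Section 6.3 does not say how a subject without a lead is analysed.

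Section 1.2 names randomization and implementation of PNS in the acute post-operative period as feasibility questions, and 6.1 says the results will refine randomization for a larger trial. The order of these steps is therefore part of what the pilot is testing.

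**Working it through.** The point rests on comparing sections; there is no stated figure to reproduce beyond the group size. Eight blocks of two give 16 subjects, 8 per group, as in Section 6 (Sample Size).

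**Randomization time, by section**
- 6.2 with 5.5: at consent, preferably before surgery, at the latest at catheter removal.
- 3.2: post-operative day 2 to 7, in subjects with moderate pain.
- Appendix with 5.5.1: Visit 1, which is catheter removal plus 1 to 2 days.

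**Time from assignment to lead.** The lead is due by day 7 (5.5.1).
- 6.2, earliest consent: catheters are typically placed the day before or the day of surgery (5.5), and 6.2 says surgery is usually next day. Day −1 to day 7 is 7 − (−1) = 8 days.
- 6.2, latest consent: day 5, with Visit 1 and the lead on day 6 or 7. The gap is 6 − 5 = 1 to 7 − 5 = 2 days.
- 3.2: from 7 − 7 = 0 up to 7 − 2 = 5 days.
- Appendix, catheter out on day 5: Visit 1 on day 6 or 7, leaving 7 − 7 = 0 to 7 − 6 = 1 day.
- Appendix, catheter out on day 3 (an example): Visit 1 on day 4 or 5, leaving up to 7 − 5 = 2 or 7 − 4 = 3 days.

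The ranges overlap. What separates 6.2 from the other two is that its preferred route puts assignment before the operation and before every Visit 1 assessment.

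**Weight of one subject.** One Group 1 subject without a lead is 1/8 = 12.5% of the group.

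**Replacement under the fix.** The documents give no Visit 1 failure rate, so q is assumed. Consented subjects needed for 16 randomized = 16/(1 − q).
- q = 5%: 16.8, so 17.
- q = 10%: 17.8, so 18.
- q = 20%: 20.
- q = one third: 24.
- q = 40%: 26.7, so 27.

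Duration = consented/(2 to 4 per month) + 12 months of follow-up.
- No failures: 16/4 + 12 = 16 to 16/2 + 12 = 20 months.
- q = 20%: 20/4 + 12 = 17 to 20/2 + 12 = 22 months.
- q = one third, slow recruitment: 24/2 + 12 = 24 months.
- q = 40%, slow recruitment: 27/2 + 12 = 25.5 months.

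The planned duration is 18 to 24 months. At the slow rate it is reached at one third failing and exceeded at 40%.

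**The case against.** The strongest reply is that this is a wording slip in a 16-subject pilot. The Appendix already shows the intended order, Visit 1 already looks for complications, and Section 8.0 names systemic infection as a reason to stop PNS. Figure 1 and some text before Section 6.0 were not available in the copy read and may show the order too.

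Part of this stands. Subjects who consent after surgery are assigned post-operatively even under 6.2, when an infection could already be known, though still before the Visit 1 baseline. Section 8.0 does address infection, but as a ground for discontinuing therapy; it does not say that a lead should not be placed. A flowchart might confirm the intended order but would leave 6.2's instruction in place.

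A reader might infer three stronger things that the documents do not support:

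- **That a lead would also be withheld for mild pain.** No text says so. Section 5.4.1 has no pain criterion and 5.5.1 sends Group 1 on to placement. Nor does 6.3 set subjects aside in one group, so any calculated shift in the group difference would measure a rule that the plan does not contain.
- **That the contrast is 8 days against 0 to 1 day.** The short gap needs catheter removal on day 5; 3.2 alone allows up to 5 days.
- **That moving the envelope removes most of the one-sidedness.** Section 5.5.2 requires test stimulation to show that the subject's pain responds, and this applies to Group 1 only, after assignment, under either timing. In the chronic-pain study described in 2.2, 14 of 16 subjects proceeded, so 2/16 = 12.5% did not. In a different setting, that is the equivalent of one subject in 8.

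**Conclusion.** The conflict is real and in current text. For subjects who consent before surgery, which is the preferred route, following 6.2 puts unblinded assignment ahead of post-operative pain, any new systemic infection and the baseline self-reports. A lead withheld for infection is then a departure from assigned treatment that can occur in Group 1 only, at 12.5% of the group per subject.

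How often this would happen, and how far knowledge of group would move baseline scores, cannot be estimated from the documents. The conclusion assumes that 6.2 is followed as written and that clinicians would withhold a lead in systemic infection. Whether moderate pain restricts entry is left open by the plan and is for the sponsor to decide. The correction should be made because it is cheap and protects the baseline; it does not make the two groups symmetric in every respect.

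**What to change.** Change 6.2 so that the envelope is opened at Visit 1, as the Appendix indicates, after the baseline assessments are complete and after a signed check, in every consented subject, that systemic infection is absent. Consent can stay before surgery. The signature should come before the envelope because, with unblinded blocks of two, the second assignment in each block is predictable.

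In addition:
- State in 5.5.1 and 5.5.2 that no lead is placed in a subject with systemic infection.
- State in 6.3 that any subject without a lead, for whatever reason, is followed and analysed in the assigned group.
- Report the number of and reasons for Visit 1 failures and for non-placements, including failed test stimulation, as feasibility results. Section 8.2 leaves screen failures out of the enrolled number, so these need their own count.
- Have the sponsor decide whether the moderate-pain condition in 3.2 is an entry criterion. If it is, add it to 5.4.1 with a named BPI item and cut-off, and apply it before the envelope is opened.

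The cost is a short amendment and one signed line at a visit that already carries these assessments. The main downside is time. With the catheter out on day 5, only 0 to 1 day remains for the check, the envelope and a procedure of up to 2 hours; earlier removal leaves longer. Visit 1 failures must also be replaced. The planned duration absorbs this at an assumed 20% failing but not at 40% with slow recruitment.
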